#### **8.3.3. Electrocardiograms**

Standard 12-lead ECGs utilizing limb leads (with a 10-second rhythm strip) should be collected at times specified in the [SoA](#) section of this protocol using an ECG machine that automatically calculates the HR and measures PR interval, QT interval, QTcF, and QRS complex. Alternative lead placement methodology using torso leads (eg, Mason-Likar) should not be used given the potential risk of discrepancies with ECGs acquired using standard limb lead placement. All scheduled ECGs should be performed after the participant has rested quietly for at least 5 minutes in a supine position.

To ensure safety of the participants, a qualified individual at the investigator site will make comparisons to baseline measurements within the respective period. Additional ECG monitoring will occur if a) a postdose QTcF interval is increased by  $\geq 60$  ms from the baseline **and** is  $> 450$  ms; or b) an absolute QT value is  $\geq 500$  ms for any scheduled ECG. If either of these conditions occurs, then 2 additional ECGs will be collected approximately 2 to 4 minutes apart to confirm the original measurement. If the QTcF values from these repeated ECGs remain above the threshold value, then a single ECG must be repeated at least hourly

until QTc values from 2 successive ECGs fall below the threshold value that triggered the repeat measurement.

If a) a postdose QTcF interval remains  $\geq 60$  ms from the baseline and is  $> 450$  ms; or b) an absolute QT value is  $\geq 500$  ms for any scheduled ECG for greater than 4 hours (or sooner, at the discretion of the investigator); or c) QTcF value get progressively longer, the participant should undergo continuous ECG monitoring. A cardiologist should be consulted if QTcF values do not return to less than the criteria listed above after 8 hours of monitoring (or sooner, at the discretion of the investigator).

In some cases, it may be appropriate to repeat abnormal ECGs to rule out improper lead placement as contributing to the ECG abnormality. It is important that leads be placed in the same positions each time in order to achieve precise ECG recordings. If a machine-read QTc value is prolonged, as defined above, repeat measurements may not be necessary if a qualified medical provider's interpretation determines that the QTcF values are in the acceptable range.

ECG values of potential clinical concern are listed in [Appendix 8](#).

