**SoA-Table 1. Study Schedule of Assessment**

Visit Identifier Abbreviations used in this table may be found in Appendix 10 .	Screening	Periods 1 and 2					ET	Follow -Up	Notes
Days Relative to Day 1	Day -28 to Day -2	Day -1 (Period 1 Only)	Day 1	Day 2	Day 3	Day 4	Day 5		28-35 days
Hours After Dose		0	48	72	96				
Physical exam	X	X					X		
 
At screening: height & body weight only.
 
Complete PE at Day -1 of Period 1; otherwise brief physical exam for findings during previous PE or new/open AEs at PI discretion.
 

Contraception use (females only)	X	X					X	X	
 
WOCBP only
 

Prior/concomitant treatments	X	X					X	X	
Single, supine 12-lead ECG	X		X				X	X	
 
Day 1 ECG: to be conducted pre-dose
 
Day 5 ECG: in Period 2 only.
 

Single, supine vital sign assessment (BP and pulse rate)	X		X				X	X	
 
Day 1 assessment: to be conducted pre-dose
 
Day 5 assessment: in Period 2 only.
 

Serious and non-serious adverse event monitoring	X	X	→	→	→	→	X	X	
Study intervention administration			X						
 
Following ≥10-hr fast; and for Period 2, a minimum 6-day interval from dosing in the previous period.
 

Urine drug test	X	X							
Urinalysis (and microscopy, if needed)	X	X					X	X	
 
Day 5: Procedures at discharge (Period 2) only.
 

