## 10.8. Appendix 8: ECG Findings of Potential Clinical Concern

ECG Findings That May Qualify as AEs

• Marked sinus bradycardia (rate <40 bpm) lasting minutes.

• New PR interval prolongation >280 ms.

• New prolongation of QTcF to >480 ms (absolute) or by <math>\geq 60</math> ms from baseline.

• New-onset atrial flutter or fibrillation, with controlled ventricular response rate: ie, rate <120 bpm.

• New-onset type I second-degree (Wenckebach) AV block of >30 seconds' duration.

• Frequent PVCs, triplets, or short intervals (<30 seconds) of consecutive ventricular complexes.

ECG Findings That May Qualify as SAEs

• QTcF prolongation >500 ms.

• New ST-T changes suggestive of myocardial ischemia.

• New-onset LBBB (QRS complex >120 ms).

• New-onset right bundle branch block (QRS complex >120 ms).

• Symptomatic bradycardia.

• Asystole:

• In awake, symptom-free participants in sinus rhythm, with documented periods of asystole <math>\geq 3.0</math> seconds or any escape rate <40 bpm, or with an escape rhythm that is below the AV node.

• In awake, symptom-free participants with atrial fibrillation and bradycardia with 1 or more pauses of at least 5 seconds or longer.

• Atrial flutter or fibrillation, with rapid ventricular response rate: rapid = rate >120 bpm.

• Sustained supraventricular tachycardia (rate >120 bpm) ("sustained" = short duration with relevant symptoms or lasting >1 minute).

• Ventricular rhythms >30 seconds' duration, including idioventricular rhythm (HR <40 bpm), accelerated idioventricular rhythm (HR >40 bpm to <100 bpm), and

monomorphic/polymorphic ventricular tachycardia (HR >100 bpm [such as torsades de pointes]).

- Type II second-degree (Mobitz II) AV block.
- Complete (third-degree) heart block.

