3.5.4. Electrocardiograms

QT interval, QTcF, PR, QRS and heart rate (HR) will be recorded at each assessment time indicated in the SoA given in the protocol. QTcF will be derived using Fridericia's heart rate correction formula:

$$\text{QTcF} = \text{QT} / (\text{RR})^{1/3} \text{ where RR} = 60/\text{HR} \text{ (if not provided)}$$

For both periods, the baseline measurement is the predose measurement on Day 1 in each period.

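### The second ECG trigger in Section 8.3.3 uses uncorrected QT, while confirmation, stopping and referral use QTcF or QTc, which leaves a narrow gap above 60 bpm

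*Protocol*

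**What the plan says.** Section 8.3.3 of the protocol lists QT and QTcF as separate outputs of the ECG machine. Its steps use the following measures.

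- **Trigger, limb (a):** postdose QTcF up by 60 ms or more from baseline, and above 450 ms.
- **Trigger, limb (b):** at any scheduled ECG, "an absolute QT value is" 500 ms or more.
- **Confirmation after two repeat ECGs:** "If the QTcF values from these repeated ECGs remain above the threshold value", hourly ECGs follow.
- **Stopping the hourly ECGs:** they run "until QTc values from 2 successive ECGs fall below the threshold value that triggered the repeat measurement".
- **Continuous monitoring:** limb (a) persisting, or uncorrected QT of 500 ms or more again, for more than 4 hours; or QTcF lengthening progressively.
- **Referral:** "A cardiologist should be consulted if QTcF values do not return to less than the criteria listed above after 8 hours of monitoring".

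On baseline, Section 8.3.3 says that a qualified person at the site "will make comparisons to baseline measurements within the respective period". SAP Section 3.5.4 agrees: "For both periods, the baseline measurement is the predose measurement on Day 1 in each period". SoA-Table 1 places ECGs at screening, predose on Day 1 of each period, Day 5 and early termination, with the note "Day 5 ECG: in Period 2 only". Protocol Appendix 8 lists "QTcF prolongation" above 500 ms as a finding that may qualify as an SAE, and new QTcF prolongation above 480 ms as one that may qualify as an AE.

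**The concern.** A trigger should be confirmed and closed on the measure that opened it. Limb (b) opens on raw QT, but site staff must then compare QTcF with a cut-off set for raw QT. The continuous-monitoring step goes back to raw QT, and referral returns to QTcF.

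Two consequences follow. At faster heart rates, raw QT under-reads relative to QTcF, so limb (b) can stay silent on a QTcF above the 500 ms that Appendix 8 treats as potentially serious. At slow rates the reverse holds: limb (b) fires on a QTcF that cannot reach 500 ms. Unless limb (a) is also met, the repeats then end, although a later rule still asks whether QT has stayed at 500 ms or more for over 4 hours.

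The schedule gives this some weight. Apart from early termination, only two scheduled ECGs follow a first dose: Period 2 Day 1 predose and Period 2 Day 5. The first is the check before re-dosing, and it rests on limb (b) alone. A high value there also raises the baseline against which Day 5 is judged.

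**Working it through.** The plan gives no figure to reproduce here. The check applies the SAP's own correction formula to the protocol's thresholds.

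**Inputs.** QTcF = QT / (60/HR)^(1/3) (SAP Section 3.5.4). Limb (a): rise of at least 60 ms and QTcF above 450 ms. Limb (b): QT of at least 500 ms (both Section 8.3.3). Eligibility ceiling for QTcF: 450 ms (Protocol Section 5.2, exclusion 10). Appendix 8 reference value: QTcF above 500 ms.

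**Step 1: QT against QTcF at 500 ms.** Here QT = QTcF × (60/HR)^(1/3).

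| HR (bpm) | QT when QTcF = 500 ms | QTcF when QT = 500 ms |
|---|---|---|
| 50 | 531.3 | 470.5 |
| 60 | 500.0 | 500.0 |
| 70 | 475.0 | 526.4 |
| 75 | 464.2 | 538.6 |
| 90 | 436.8 | 572.4 |

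Above 60 bpm, a QTcF of 500 ms has a QT below 500 ms, so limb (b) does not fire.

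**Step 2: what limb (a) picks up postdose.** For QTcF above 500 ms it fires when QTcF is at least baseline + 60. A baseline of 440 ms or less leaves nothing uncovered, because 440 + 60 = 500. Above that, the uncovered range runs from 500 ms to just under baseline + 60:

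- baseline 445 ms: to just under 505 ms
- baseline 450 ms: to just under 510 ms
- baseline 460 ms: to just under 520 ms
- baseline 470 ms: to just under 530 ms

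The 460 and 470 ms baselines are illustrative assumptions. They exceed the eligibility ceiling, but Section 8.3.3 sets no ceiling on a Period 2 predose baseline.

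**Step 3: does limb (b) rescue these values?** Take QTcF 509 ms with baseline 450 ms; the rise is 59 ms, so limb (a) is not met. QT falls below 500 ms at any rate above 60 × (509/500)^3 = 63.3 bpm. At 75 bpm, QT is 509 × (60/75)^(1/3) = 472.5 ms; at 90 bpm it is 444.7 ms. With the assumed 470 ms baseline, QTcF 529 ms at 75 bpm is QT 491.1 ms. Neither limb fires in any of these cases. Just above 60 bpm the range is shorter, because QT itself soon reaches 500 ms: with baseline 450 ms it ends at about 502.7 ms at 61 bpm and 505.4 ms at 62 bpm.

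**Step 4: Period 2 Day 1 predose.** This recording is the period baseline, so limb (a) cannot apply. From the table, limb (b) alone stays silent up to a QTcF of about 526 ms at 70 bpm, 538 ms at 75 bpm and 572 ms at 90 bpm.

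**Step 5: slow rates.** At 50 bpm, QT 500 ms is QTcF 470.5 ms and QT 510 ms is QTcF 479.9 ms. QT must reach 531.3 ms before QTcF reaches 500 ms. Between QT 500 and 531 ms, limb (b) fires, but a QTcF cut-off of 500 ms cannot confirm it.

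**Step 6: with limb (b) as QTcF of at least 500 ms.** The missed region is empty at every heart rate and every baseline.

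**The case against.** The strongest reply is that limb (b) is a wording slip for absolute QTcF. Section 8.3.3 closes by speaking of a prolonged machine-read QTc as already defined, Appendix 8 applies the word absolute to QTcF, and exclusion 10 makes QTcF the basis for eligibility decisions. On that reading the gap disappears. This is plausible, but it shows what the text should say. The rule that staff must follow still says QT, in two places, in a section that separates QT from QTcF.

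It is also fair that the number 500 ms is available for stopping, through the reference to the triggering threshold. What is missing is the measure to which it applies.

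The point on materiality largely stands. Unscheduled safety measurements are allowed (Section 8.3), abnormal ECGs may be repeated, the investigator may escalate sooner, and Appendix 8 flags QTcF above 480 or 500 ms. The postdose gap needs a baseline above 440 ms, a rise under 60 ms and a rate above 60 bpm; apart from early termination, the one scheduled ECG at which it can arise is 96 hours after a single 80 mg dose. A predose value of 526 ms would lie 76 ms above the eligibility ceiling, at least 6 days after one dose. Section 2.2.4.1 reports no clinically significant adverse ECG trends in the completed studies. These safeguards are discretionary or concern reporting, however. They do not replace the mandatory repeat-and-monitor step.

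Finally, replacing QT by QTcF gives up a prompt at slow rates: at 50 bpm, QT from 500 to 531 ms would no longer trigger. That cost is real but small.

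**Conclusion.** The concern holds on the text as written. Limb (b) triggers on one measure and is confirmed, stopped and referred on another, and Section 8.3.3 has no absolute QTcF trigger. Within the eligibility ceiling, the postdose gap is at most QTcF above 500 to just under 510 ms, at rates above 60 bpm; it widens only if a Period 2 baseline exceeds 450 ms, which is an assumption. At the Period 2 predose ECG the blind range is wider, but it needs a value well above anything eligible at entry. What is lost is the automatic repeat and monitoring, since Appendix 8 would still flag these values. The primary endpoints are not affected, and the SAP plans no ECG summary (Section 6.6.4). This is a minor correction to a safety rule, worth making because it is so cheap.

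**What to change.** In both places in Section 8.3.3 where limb (b) appears, state the criterion as an absolute QTcF of 500 ms or more. Add one sentence saying that confirmation, stopping of the hourly repeats, continuous monitoring and cardiologist referral for limb (b) all use QTcF of 500 ms or more. In the stopping rule, write QTcF for QTc.

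If the sponsor wishes to keep the prompt at slow heart rates, wording limb (b) as QT or QTcF of 500 ms or more is also acceptable, provided the later steps say which measure closes each trigger.

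The cost is two phrase replacements, one abbreviation and one sentence. No ECGs are added, and the machine already reports QTcF.

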#### **8.3.4. Clinical Safety Laboratory Assessments**

See [Appendix 2](#) for the list of clinical safety laboratory tests to be performed and the [SoA](#) for the timing and frequency. All protocol-required laboratory assessments, as defined in [Appendix 2](#), must be conducted in accordance with the laboratory manual and the [SoA](#). Unscheduled clinical laboratory measurements may be obtained at any time during the study to assess any perceived safety issues.

The investigator must review the laboratory report, document this review, and record any clinically significant changes occurring during the study in the AE section of the CRF. Clinically significant abnormal laboratory test findings are those that are not associated with the underlying disease, unless judged by the investigator to be more severe than expected for the participant's condition.

All laboratory tests with values considered clinically significant and abnormal during participation in the study or within 5 days after the last dose of study intervention should be repeated until the values return to normal or baseline or are no longer considered clinically significant by the investigator or study medical monitor.

If such values do not return to normal/baseline within a period of time judged reasonable by the investigator, the etiology should be identified and the sponsor notified.

See [Appendix 6](#) for suggested actions and follow-up assessments in the event of potential DILI.

See [Appendix 7](#) for instructions for laboratory testing to monitor kidney function and reporting laboratory test abnormalities.

Participants may undergo random urine drug testing at the discretion of the investigator. Drug testing conducted prior to dosing must be negative for participants to receive study intervention.

### **8.3.5. COVID-19 Specific Assessments**

Assessment of risk for, symptoms of, or testing for COVID-19 may be performed at admission to the CRU, and/or at other times during the study at investigator discretion and according to local site policies.

### **8.3.6. Pregnancy Testing**

A serum pregnancy test is required at screening. Following screening, pregnancy tests may be urine or serum tests, and must have a sensitivity of at least 25 mIU/mL. Pregnancy tests will be performed in WOCBP at the times listed in the [SoA](#). Following a negative pregnancy test result at screening, appropriate contraception must be commenced and a second negative pregnancy test result will be required at the baseline visit prior to the participant's receiving the study intervention. Pregnancy tests will also be done whenever 1 menstrual cycle is missed during the active treatment period (or when potential pregnancy is otherwise suspected) and at the end of the study. Pregnancy tests may also be repeated if requested by IRBs/ECs or if required by local regulations.

## **8.4. Adverse Events, Serious Adverse Events, and Other Safety Reporting**

The definitions of an AE and an SAE can be found in [Appendix 3](#).

AEs may arise from symptoms or other complaints reported to the investigator by the participant (or, when appropriate, by a caregiver, surrogate, or the participant's legally authorized representative), or they may arise from clinical findings of the investigator or other healthcare providers (clinical signs, test results, etc).

The investigator and any qualified designees are responsible for detecting, documenting, and recording events that meet the definition of an AE or SAE and remain responsible to pursue and obtain adequate information both to determine the outcome and to assess whether the event meets the criteria for classification as an SAE or caused the participant to discontinue the study (see [Section 7.1](#)).

During the active collection period as described in Section 8.4.1, each participant will be questioned about the occurrence of AEs in a nonleading manner.

In addition, the investigator may be requested by Pfizer Safety to obtain specific follow-up information in an expedited fashion.

### **8.4.1. Time Period and Frequency for Collecting AE and SAE Information**

The time period for actively eliciting and collecting AEs and SAEs ("active collection period") for each participant begins from the time the participant provides informed consent, which is obtained before undergoing any study-related procedure and/or receiving study

intervention), through and including a minimum of 28 calendar days, except as indicated below, after the last administration of the study intervention.

Follow-up by the investigator continues throughout the active collection period and until the AE or SAE or its sequelae resolve or stabilize at a level acceptable to the investigator.

When a clinically important AE remains ongoing at the end of the active collection period, follow-up by the investigator continues until the AE or SAE or its sequelae resolve or stabilize at a level acceptable to the investigator and Pfizer concurs with that assessment.

For participants who are screen failures, the active collection period ends when screen failure status is determined.

If the participant withdraws from the study and also withdraws consent for the collection of future information, the active collection period ends when consent is withdrawn.

If a participant permanently discontinues or temporarily discontinues study because of an AE or SAE, the AE or SAE must be recorded on the CRF and the SAE reported using the CT SAE Report Form.

Investigators are not obligated to actively seek information on AEs or SAEs after the participant has concluded study participation. However, if the investigator learns of any SAE, including a death, at any time after a participant has completed the study, and they consider the event to be reasonably related to the study intervention, the investigator must promptly report the SAE to Pfizer using the CT SAE Report Form.

#### **8.4.1.1. Reporting SAEs to Pfizer Safety**

All SAEs occurring in a participant during the active collection period as described in [Section 8.4.1](#) are reported to Pfizer Safety on the CT SAE Report Form immediately upon awareness and under no circumstance should this exceed 24 hours, as indicated in [Appendix 3](#). The investigator will submit any updated SAE data to the sponsor within 24 hours of its being available.

#### **8.4.1.2. Recording Nonserious AEs and SAEs on the CRF**

All nonserious AEs and SAEs occurring in a participant during the active collection period, which begins after obtaining informed consent as described in [Section 8.4.1](#), will be recorded on the AE section of the CRF.

The investigator is to record on the CRF all directly observed and all spontaneously reported AEs and SAEs reported by the participant.

As part of ongoing safety reviews conducted by the sponsor, any nonserious AE that is determined by the sponsor to be serious will be reported by the sponsor as an SAE. To assist in the determination of case seriousness, further information may be requested from the investigator to provide clarity and understanding of the event in the context of the clinical study.

Reporting of AEs and SAEs for participants who fail screening are subject to the CRF requirements as described in [Section 5.4](#).

#### **8.4.2. Method of Detecting AEs and SAEs**

The method of recording, evaluating, and assessing causality of AEs and SAEs and the procedures for completing and transmitting SAE reports are provided in [Appendix 3](#).

Care will be taken not to introduce bias when detecting AEs and/or SAEs. Open-ended and nonleading verbal questioning of the participant is the preferred method to inquire about AE occurrences.

#### **8.4.3. Follow-Up of AEs and SAEs**

After the initial AE or SAE report, the investigator is required to proactively follow each participant at subsequent visits/contacts. For each event, the investigator must pursue and obtain adequate information until resolution, stabilization, the event is otherwise explained, or the participant is lost to follow-up (as defined in [Section 7.3](#)).

In general, follow-up information will include a description of the event in sufficient detail to allow for a complete medical assessment of the case and independent determination of possible causality. Any information relevant to the event, such as concomitant medications and illnesses, must be provided. In the case of a participant death, a summary of available autopsy findings must be submitted as soon as possible to Pfizer Safety.

Further information on follow-up procedures is provided in [Appendix 3](#).

#### **8.4.4. Regulatory Reporting Requirements for SAEs**

Prompt notification by the investigator to the sponsor of an SAE is essential so that legal obligations and ethical responsibilities toward the safety of participants and the safety of a study intervention under clinical investigation are met.

The sponsor has a legal responsibility to notify both the local regulatory authority and other regulatory agencies about the safety of a study intervention under clinical investigation. The sponsor will comply with country-specific regulatory requirements relating to safety reporting to the regulatory authority, IRBs/ECs, and investigators.

Investigator safety reports must be prepared for SUSARs according to local regulatory requirements and sponsor policy and forwarded to investigators as necessary.

An investigator who receives SUSARs or other specific safety information (eg, summary or listing of SAEs) from the sponsor will review and then file it along with the SRSD(s) for the study and will notify the IRB/EC, if appropriate according to local requirements.

#### **8.4.5. Environmental Exposure, Exposure During Pregnancy or Breastfeeding, and Occupational Exposure**

Environmental exposure, occurs when a person not enrolled in the study as a participant receives unplanned direct contact with or exposure to the study intervention. Such exposure may or may not lead to the occurrence of an AE or SAE. Persons at risk for environmental exposure include healthcare providers, family members, and others who may be exposed. An environmental exposure may include EDP, EDB, and occupational exposure.

Any such exposures to the study intervention under study are reportable to Pfizer Safety within 24 hours of investigator awareness.

